2.7.1 Adverse events (AEs)

Summary tables for adverse events (AEs) will include all AEs that started or worsened during the on-treatment period, including acute Graft-versus-Host Disease (GvHD) and chronic GvHD. When specified, some AEs summaries will include all AEs occurring during the overall safety period.

The number (and percentage) of participants with treatment emergent adverse events will be summarized by primary system organ class (SOC), preferred term (PT) and maximum CTCAE grade. A participant with multiple occurrences of an AE will be counted only once in the respective AE category. A participant with multiple CTCAE grades for the same PT will be summarized under the maximum CTCAE grade recorded for the event. AEs will be assessed according to the Common Terminology Criteria for Adverse Events (CTCAE) version 5.0.

In the AE summaries, the primary SOC will be presented alphabetically, and the PT will be sorted within primary SOC in descending frequency. The sort order for the PT will be based on their frequency in the highest dose level of sabatolimab. The summaries will show 'All grades' (including AEs with missing grade) and 'Grades ≥ 3 '.

The following adverse event summaries will be produced selecting all or a subset of AEs depending on seriousness, relationship to study drugs, and outcome or action taken:

- AEs (by SOC and by PT) and separately those considered related to study drugs
- SAEs
- SAEs with the number of occurrences (an occurrence is defined as > 1 day between start and prior end date of record of same PT)
- Non-SAEs
- SAEs with fatal outcome
- AEs leading to sabatolimab permanent discontinuation

In addition, all AEs and SAE by SOC and PT will be provided on the overall safety period. All reported AEs will be listed and those that started during the pre-treatment, on-treatment and post-treatment period will be flagged.

2.7.1.1 Grade III or IV aGvHD and moderate to severe cGvHD

Separate listings including information on the maximum GvHD stage by organ will be provided for:

- treatment emergent grade III or grade IV acute GvHD
- treatment emergent moderate to severe chronic GvHD

2.7.1.2 Severe immune-related adverse events not attributed to GvHD

Treatment-emergent \geq grade 3 immune-related adverse events not attributed to GvHD will be described in the AE listing.

2.7.1.3 Adverse events of special interest / grouping of AEs

An adverse event of special interest is a grouping of adverse events that are of scientific and medical concern specific to the compound sabatolimab. These groupings are defined using

Novartis	
SAP – Amendment 1	

MedDRA terms, SMQs (standardized MedDRA queries), HGLTs (high level group terms), HLT (high level terms) and PTs (preferred terms). Customized SMQs (Novartis MedDRA queries, NMQ; and Customized MedDRA queries, CMQ) may also be used. NMQ and CMQ are a customized group of search terms which defines a medical concept for which there is no official SMQ available or the available SMQ does not completely fit the need. Unlike a NMQ, the CMQ is more specific for a particular compound. Both may include a combination of single terms and/or an existing SMQ, narrow or broad. These searches will be defined in the eCRS (electronic Case Retrieval Strategy) in the DMS (Document Management System) and a listing of search terms will be provided in the CSR.

For each specified AESI, the number (%) of participants with at least one event of the AESI occurring during the on-treatment period will be summarized together with the individual preferred terms in that grouping.

2.7.2 Deaths

Separate summaries for on-treatment and all deaths (including post-treatment deaths not in the AE CRF but in the survival CRF) will be produced showing deaths reasons by SOC and PT. All deaths will be listed; post treatment deaths will be flagged. A separate listing of deaths prior to starting treatment will be provided for all screened participants.

2.7.3 Laboratory data

Grading of laboratory values will be assigned programmatically as per National Cancer Institute (NCI) Common Terminology Criteria for Adverse Events (CTCAE) version 5.0. The calculation of CTCAE grades will be based on the observed laboratory values only, clinical assessments will not be taken into account.

CTCAE Grade 0 will be assigned for all non-missing values not graded as 1 or higher.

For laboratory tests where grades are not defined by CTCAE v5.0, results will be categorized as low/normal/high based on laboratory normal ranges.

For laboratory tests where grades are defined by CTCAE v5.0:

• Shift tables using CTCAE v5.0 grades to compare baseline to the worst on-treatment value

Liver function parameters of interest are total bilirubin, alanine aminotransferase (ALT), aspartate aminotransferase (AST) and alkaline phosphatase. The number (%) of participants with worst post-baseline values as per Novartis Liver Toxicity guidelines will be summarized.

All CTCAE grade 3 or 4 laboratory toxicities will be listed.

2.7.4 Other safety data

Safety data listed in this section will be listed for the safety set and presented by dose cohort (Adults with sabatolimab 400 mg, Adults with sabatolimab 800 mg, Adults with azacitidine and sabatolimab combination, Adolescents with sabatolimab monotherapy) and by visit/sampling timepoint.

2.7.4.1 ECG

Local ECGs are performed at screening, end of treatment and as clinically indicated. If abnormalities are observed based on these local ECGs, these abnormalities are to be reported and thus summarized as AEs.

2.7.4.2 Vital signs

Vital sign values during the on-treatment period will be listed.

2.8 Pharmacokinetic endpoints

2.8.1 Sabatolimab drug concentrations

Pharmacokinetic analyses will be summarized for the sabatolimab pharmacokinetic analysis set. Sabatolimab concentration data will be listed by participant, and visit/sampling time point. Descriptive statistics (n, m (number of non-zero concentrations), mean, coefficient of variation (CV%), standard deviation, median, geometric mean, geometric CV%, minimum and maximum) for sabatolimab will be presented at each scheduled timepoint. Below the limit of quantitation (BLQ) values will be set to zero by the Bioanalyst and will be displayed in the listing of all PK concentrations as zero and flagged. However, BLQ values will be treated as missing for the calculation of the geometric means and geometric CV% but included as zero in the other summary statistics. Missing values for PK concentrations will not be imputed and will be treated as missing.

2.10 Interim analysis

Interim analyses are planned for the monitoring of safety data, and will be conducted after each dose level cohort of the safety run-in part to determine the recommended dose for expansion (RDE):

- One meeting after participants included in the first cohort (treated with sabatolimab at the 400 mg Q4W) have completed 2 cycles of treatment,
- A second meeting after participants included in the second cohort (treated with sabatolimab at 800 mg Q4W) have completed 2 cycles of treatment.

The decision to start enrollment in the second cohort and to continue with the sabatolimab dose of 800 mg Q4W in the expansion phase will be guided by a Bayesian analysis based on the incidence of dose limiting toxicity (DLT) data.

For each cohort (sabatolimab 400 mg and 800 mg Q4W) of the safety run-in part, the following information (summaries and/or listings) will be provided:

- Number (%) of participants treated and included in the analysis sets
- Basic demographic and background data
- Disease characteristics (including ELN risk category)
- Medical history
- Prior and concomitant medications (including immunosuppressive treatments)
- Participant disposition

- Protocol deviations
- Duration of exposure to study treatment
- Dose intensity and relative dose intensity
- Number (%) of participants with any dose changes (including reductions, interruptions, or permanent discontinuations) and the reasons
- DLTs, AEs, treatment related AEs, SAEs, on-treatment deaths reported during the DLT evaluation period, as well as DLTs, AEs, treatment related AEs, SAEs, on-treatment deaths reported up to the data cut-off date
- AESI overview (if AESI definition is available at the time of the safety review meetings)
- Posterior distribution for the risk of DLT for new participants at the dose level tested (see Section 2.5)
- Laboratory data and vital signs abnormalities
- Investigator's response assessment
- Sabatolimab concentrations (if available)

For the regular safety review meetings conducted after the safety run-in part, the same information as listed above will be provided except the investigator's response assessment as this information is only used for decision making on the RDE.

The exact list of tables, listings and figures prepared for those safety review meetings will be defined in a separate planning document (e.g. TFL).

3 Sample size calculation

Primary safety analysis (incidence of dose-limiting toxicity)

No formal statistical power calculations to determine sample size were performed for the safety run-in part.

A cohort of 6 to 8 participants will be enrolled in the first cohort treated with sabatolimab at 400 mg Q4W dose level and a cohort of 9 to 12 participants will be enrolled in the second cohort treated with sabatolimab at 800 mg Q4W dose level.

In the context of this intrinsic risk of GvHD, the definition of an acceptable level of toxicity does not follow the EWOC criterion (i.e. probability to observe a DLT rate exceeding 33% is below 25%) as defined in a standard oncology Phase I study. Thus, instead of considering a 33% threshold for the probability to observe a DLT rate, 50% will be selected as the threshold to qualify for an acceptable toxicity (i.e. probability to observe a DLT rate exceeding 50% is below 25%).

Data scenarios for the incidence of DLTs in the two cohorts of the safety run-in part, including the decision made based on the dose-DLT Bayesian logistic regression model, as well as operating characteristics, are presented in Appendix 16.6 of the protocol.

Primary efficacy analysis (proportion of participants with no hematologic relapse)

The sample size calculation is based on the proportion of participants reported with no evidence of hematologic relapse (i.e. maintenance of CR or CRi), defined as absence of bone marrow blasts \geq 5%; absence of reappearance of blasts in the blood; and absence of the development of

extramedullary disease after 6 cycles of treatment. The hypotheses to be tested and details of the testing strategy for each of the study treatment (sabatolimab in monotherapy and sabatolimab in combination with azacitidine) are described in Section 2.5.2.

A sample size of 25 adults, from both the safety-run and expansion monotherapy cohorts treated with sabatolimab in monotherapy at the recommended dose for expansion (RDE), is required to meet both statistical significance (posterior probability that the proportion of adult participants who remain with no evidence of hematologic relapse $\geq 15\%$ is greater or equal to 97.5%) and clinical relevance (posterior probability that the proportion of adult participants who remain with no evidence of hematologic relapse $\geq 30\%$ is greater or equal to 50%). At least 8 participants who remain with no evidence of hematologic relapse after 6 cycles of treatment out of 25 participants treated with sabatolimab in monotherapy are required for success (both statistical significance and clinical relevance met).

A sample size of 20 adult participants treated with sabatolimab in combination with azacitidine (combination cohort) is required to meet both statistical significance (posterior probability that the proportion of participants with no evidence of hematologic relapse $\geq 30\%$ is greater or equal to 97.5%) and clinical relevance (posterior probability that the proportion of participants with no evidence of hematologic relapse $\geq 50\%$ is greater or equal to 50%). At least 11 participants, who remain with no evidence of hematologic relapse after 6 cycles of treatment out of 20 participants treated with sabatolimab in combination with azacitidine, are required for success (both statistical significance and clinical relevance met).

Data scenarios including the decisions for different values of the proportion of participants with no hematologic relapse, as well as operating characteristics, are presented in Section 12.8 of the protocol.

4 Change to protocol specified analyses

Not applicable.

5 Appendix

5.1 General definitions

Date of first administration of study drug (sabatolimab) or azacitidine

The date of first administration of study drug (sabatolimab) or azacitidine is defined as the first date when a non-zero dose of the respective study drug or azacitidine is administered and recorded on the study treatment eCRF page.

Date of last administration of study drug (sabatolimab) or azacitidine

The date of the last administration of the study drug (sabatolimab) or azacitidine is defined as the last date when a non-zero dose of the respective study drug or azacitidine is administered and recorded on the study treatment eCRF page. So both, first and last date of study drug, are derived separately for each drug which is part of the study treatment.

Novartis	Confidential	Page 33 of 35
SAP – Amendment 1		CMBG453F12201

Date of first administration of study treatment (combination cohort)

The date of the first administration of study treatment (or the start date of study treatment) is defined as the first date when a non-zero dose of any component of the study treatment (sabatolimab or azacitidine) is administered.

Date of last administration of study treatment (combination cohort)

The date of the last administration of study treatment (or the end date of study treatment) is defined as the last date when the last non-zero dose of any last component of the study treatment (sabatolimab or azacitidine) is administered.

Date of last exposure to study drug (sabatolimab) or azacitidine

One planned cycle length is 28 days and the start date of a cycle is defined as the first administration of sabatolimab within a cycle in cohorts when administered in monotherapy (Cohorts 1, 2, 4, and 5) and as the first administration of azacitidine within a cycle in the combination cohort (Cohort 3). Sabatolimab, when administered in monotherapy, is administered every 4 weeks (Q4W), on Day 1 of each cycle, unless there was a toxicity leading to a dosing interval increase. Sabatolimab, when administered in combination with azacitidine, is administered every 4 weeks (Q4W), on Day 5 of each cycle, unless there was a toxicity leading to a dosing interval increase. Azacitidine is planned to be administered daily every cycle during the first 5 days of each cycle (Day 1 to Day 5).

As treatment is given in cycles, the date of the last administration of study treatment is not considered the date of the last exposure but instead the planned end date of the last cycle in which the last non-zero dose was given.

The date of last exposure to sabatolimab is therefore calculated as:

• If sabatolimab is given Q4W: Minimum (last date of administration of sabatolimab + 27 days, date of death, last contact date in case participant is lost to follow-up, data cut-off date).

The date of last exposure to azacitidine is calculated as:

• Minimum (the last date of administration of azacitidine + 23 days, date of death, the last contact date in case participant is lost to follow-up, data cut-off date) as azacitidine doses are given daily every cycle during 5 days at the beginning of each cycle (between Day1 to Day 5).

The date of last exposure to study treatment (sabatolimab and azacitidine) is defined as:

• The latest date among the last date of exposure to sabatolimab and azacitidine treatment. This date will be taken to derive duration of exposure to study treatment (sabatolimab and azacitidine).

End date of the last cycle initiated

The end date of the last cycle initiated is the planned end date (Day 28) of the last cycle initiated when the last non-zero dose of any last component of the study treatment (sabatolimab or azacitidine) is administered.

Novartis	Confidential	Page 34 of 35
SAP – Amendment 1		CMBG453F12201

The end date of the last cycle initiated (Day 28 or beyond) will be applicable even if this date goes beyond the data cut-off date (i.e. it should not be truncated to the date of data cut-off).

Date of last exposure and duration of exposure to study treatment (combination cohort)

For the calculation of the duration of exposure to study treatment (combination), the date of the last exposure to study treatment (combination) will be derived as the minimum date between:

- The date of last exposure to study treatment,
- Date of death,
- Last contact date in case the participant is lost to follow-up.

The duration of exposure to study treatment (combination) will be calculated as follows: date of last exposure to study treatment (combination) - date of first administration of study treatment (combination) + 1.

Duration from first to last cycle initiated to calculate dose intensity and the relative dose intensity

For the calculation of the dose intensity and relative dose intensity, the duration in days from first to last cycle initiated will be calculated as follow: date of last exposure - date of first administration of study treatment (combination) + 1.

Thus, this derivation will be irrespective of date of death or last contact date (i.e. it should not be truncated to the date of death or date of last contact date).

Study day

The study day, describes the day of the event or assessment date, relative to the reference start date (start date of study treatment).

The study day is calculated as follows:

- The date of the event (visit date, onset date of an event, assessment date etc.) reference start date + 1 if event is on or after the reference start date;
- The date of the event (visit date, onset date of an event, assessment date etc.) reference start date if event precedes the reference start date.

The reference start date for safety assessments (e.g. adverse event onset, laboratory or ECG assessment, vital sign measurement etc.) is the start of study treatment. The same reference start date will be used for efficacy (e.g. response assessment, time-to-event endpoints).

The study day will be displayed in the data listings. If an event starts before the reference start date, the study day displayed on the listing will be negative.

Time unit

A year length is defined as 365.25 days. A month length is 30.4375 days (365.25/12). If duration is reported in months, duration in days will be divided by 30.4375. If duration is reported in years, duration in days will be divided by 365.25.

Baseline

For efficacy evaluations, the last non-missing assessment, including unscheduled assessments on or before the date of start of study treatment is taken as "baseline" value or "baseline" assessment.

For safety evaluations, the last available assessment including unscheduled assessments on or before the date of start of study treatment is taken as "baseline" assessment.

If participants have no value as defined above, the baseline result will be missing.

Laboratory parameter derivations

If laboratory values are provided as '<X' (i.e. below limit of detection) or '>X', prior to conversion of laboratory values to SI unit, these numeric values are set to X.

The following rules will be applied to derive the WBC differential counts when only percentages are available for a xxx differential

xxx count = (WBC count) * (xxx %value / 100)

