6.6 Additional treatment guidance

6.6.1 Treatment compliance

Every time the investigational treatment sabatolimab is to be administered, IRT must be accessed to assign a medication (kit) number to the participants. The date and time of all study treatment administration sabatolimab during the study and any deviations from the protocol treatment schedule will be captured by the investigator staff and reviewed by field monitor on the appropriate study treatment dispensing form. Compliance with the study treatment will be assessed by the field monitor at each visit and information provided by the pharmacist or by the investigator. All study treatment dispensed, returned or destroyed as per local regulation must be recorded in the Drug Accountability Log.

Pharmacokinetic parameters will be determined in all participants as detailed in the pharmacokinetics Section 8.5.2.

All dosages for sabatolimab as well as azacitidine (Combination cohort) prescribed to the participant and all dose changes during the study must be recorded on the corresponding Dosage Administration Record.

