2.7 Safety analyses

Safety analyses will be summarized for the safety set and by dose cohort (adults with sabatolimab 400 mg, adults with sabatolimab 800 mg, adults with azacitidine & sabatolimab combination, adolescents with sabatolimab monotherapy).

Safety summaries (tables) include only data from the on-treatment period with the exception of baseline data which will also be summarized where appropriate (e.g. change from baseline summaries). In addition, a separate summary for death including on treatment and post treatment deaths will be provided. In particular, summary tables for adverse events (AEs) will summarize only on-treatment events, with a start date during the on-treatment period (treatment-emergent AEs). Listings will be also provided.

The overall observation period will be divided into three mutually exclusive segments:

- 1. Pre-treatment period: from day of participant's informed consent to the day before the first administration of study treatment
- 2. On-treatment period: from the date of the first administration of study treatment to 30 days after the date of the last administration of study treatment
- 3. Post-treatment period: any observation starting at day 31 after the last administration of study treatment

An overall safety period will be defined from date of the first administration of study treatment to 150 days after the last dose of sabatolimab.

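### The safety baseline and the on-treatment period share the calendar date of first dose, so laboratory shift tables cannot show improvement and a post-dose Day 1 test can become the baseline

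*SAP*

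**What the plan says.** Three rules in the SAP meet on Cycle 1 Day 1.

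- **Baseline (SAP 5.1).** "For safety evaluations, the last available assessment including unscheduled assessments on or before the date of start of study treatment is taken as" baseline. The start is a calendar date: the "first date when a non-zero dose of any component of the study treatment (sabatolimab or azacitidine) is administered". The rule carries no clock time and no requirement that the sample precede the dose.
- **Periods (SAP 2.7).** "The overall observation period will be divided into three mutually exclusive segments". The pre-treatment segment runs from consent "to the day before the first administration of study treatment". The next is defined as "On-treatment period: from the date of the first administration of study treatment to 30 days after the date of the last administration of study treatment". Protocol 12.5.2 uses the same day-based segments.
- **Shift tables (SAP 2.7.3).** "Shift tables using CTCAE v5.0 grades to compare baseline to the worst on-treatment value". In the same section, the liver summary uses the worst post-baseline value instead.

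On the data side, Protocol Tables 8-1 and 8-2 schedule hematology and chemistry on Cycle 1 Day 1. Protocol 8.3.1 states that the Day 1 hematology is pre-dose; we found no such statement for chemistry. Protocol 8.4.1 allows unscheduled laboratory tests whenever clinically indicated.

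**The concern.** The three segments are mutually exclusive, but baseline is not tied to the pre-treatment one. All Day 1 values fall in the on-treatment segment, including the pre-dose sample that SAP 5.1 makes the baseline. One record then sits on both sides of the shift table. The SAP also has no rule to stop a test drawn after dosing on Day 1 from displacing the pre-dose value as the last one available on that date.

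Changes in laboratory values are part of a secondary safety endpoint that SAP Table 1-1 retains for the final report. The SAP revision history records that the hematology figures and their tables were deleted, so the shift tables carry more of the hematology reporting. Abnormal baselines are to be expected: Protocol 5.1 admits platelets down to 75 x 10^9/L, ANC down to 1.0 x 10^9/L, hemoglobin down to 8 g/dL and AST/ALT up to 3 x ULN.

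**Working it through.** No figure in either document depends on this rule, so there is nothing to reproduce. The check is one of logic, followed by an illustration of size.

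**1. Where each record falls**

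| Record | Baseline (SAP 5.1) | Period (SAP 2.7) |
|---|---|---|
| Screening sample | Only if there is no Day 1 value | Pre-treatment |
| Cycle 1 Day 1, pre-dose | Yes, unless a later test follows that day | On-treatment |
| Cycle 1 Day 1, unscheduled, post-dose | Yes, as the last value on that date | On-treatment |

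**2. Pre-dose sample counted on both sides.** Let b be the baseline grade and w the worst grade among later on-treatment samples. The tabulated worst grade is W = max(b, w).

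- Improvement requires W < b, which is impossible. Those cells are empty by construction.
- Worsening requires W > b, which holds exactly when w > b. Worsening counts are the same with or without the overlap.
- With no later sample, W = b. The participant is shown as unchanged, although the later value is missing.

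A participant's entry changes only if b is worse than every later grade or if there is no later sample.

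**3. Illustration of the lost improvement cells (platelets).** Let k be the number of scheduled hematology samples after Cycle 1 Day 1 on the monotherapy schedule: 3 to the end of Cycle 2 (Days 15, 1 and 15), 3 + 4 = 7 to Cycle 6, and 3 + 22 = 25 to Cycle 24. If a participant's values are exchangeable over time (no drift), baseline is strictly the worst of k + 1 values with probability at most 1/(k + 1).

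The simulation uses inputs that are assumptions, not document figures: lower limit of normal 150, further grade cuts at 75, 50 and 25, median 140 x 10^9/L, between-person log-SD 0.4, within-person log-SD 0.15 or 0.30, and log drift 0 or +0.2. Only the entry limit of 75 is from the protocol, and it is applied to the baseline value.

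| k | 1/(k + 1), no drift | Improved, baseline record excluded | Improved, baseline record included |
|---|---|---|---|
| 3 | 25.0% | 2.5% to 11.8% | 0% |
| 7 | 12.5% | 1.0% to 6.8% | 0% |
| 25 | 3.8% | 0.2% to 2.8% | 0% |

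The share that worsened was identical under both definitions in every setting. With log-SD 0.15, no drift and k = 7, it was 29.6% either way.

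**4. Post-dose test taken as baseline.** Suppose the pre-dose grade is 0 and a test after the infusion on Day 1 is grade 3. SAP 5.1 selects the grade 3 value. If no later value is worse, the table shows 3 to 3 where the true shift is 0 to 3. The liver summary is also exposed: a Day 1 peak that has become the baseline is no longer post-baseline. The documents give no frequency for such tests.

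**The case against.** **Baseline may be meant to stand apart.** SAP 2.7 and Protocol 12.5.2 restrict safety summaries to on-treatment data, with baseline data as a stated exception, and the liver summary already uses post-baseline values. A programmer might therefore leave the baseline record out of the shift tables. That is plausible, but neither sentence does it. The exception allows baseline data to be summarized as well; it does not remove a Day 1 record from the on-treatment values. The liver wording applies only to the liver summary.

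**The double count is mild.** This stands. A reader might infer that it inflates on-treatment toxicity or hides deterioration. Step 2 shows that it does neither. A pre-existing grade 2 does enter the worst on-treatment margin, but the table prints the baseline grade beside it, so a 2 to 2 entry is visibly pre-existing.

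**The post-dose route is narrow.** This also stands in large part. Scheduled Day 1 hematology is pre-dose, so the route needs a discretionary test or chemistry drawn after dosing. Table 6-3 does not call for repeat laboratory tests in an infusion reaction. In the combination cohort, treatment starts with azacitidine and Protocol 6.1.1 does not allow Cycle 1 sabatolimab before Day 5, so a sabatolimab infusion reaction cannot fall on the baseline date there. A reader might infer that acute toxicity would vanish from the report. It would not: SAP 2.7.3 lists all grade 3 or 4 laboratory values, Protocol 10.1.1 makes clinically significant abnormalities adverse events, and DLTs are investigator-assessed. The remaining gap is a milder change, such as 0 to 2 shown as 2 to 2, that was not reported as an adverse event.

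**Conclusion.** The point holds as a minor fault in stated rules. Read as written, SAP 5.1, 2.7 and 2.7.3 make a Cycle 1 Day 1 pre-dose sample both baseline and on-treatment. The shift tables lose their improvement cells and show a participant with no later sample as unchanged. The direction of that loss is certain on the literal reading. Its size is not: the percentages above depend on assumed platelet behavior and shrink as samples accumulate.

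The second effect, a post-dose Day 1 value serving as baseline, is the only one that can mask worsening, and its frequency is unknown.

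A reader might want to turn either effect into a number of affected participants. The documents do not support that. They give no baseline abnormality rates or rates of return to grade, and the SAP states that recruitment was halted with limited numbers, so the planned cohort sizes cannot serve as denominators. No primary endpoint, decision rule, dose decision or error rate depends on these descriptive tables.

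**What to change.** Make two wording changes together.

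1. **SAP 5.1.** Define the safety baseline as the last assessment before the first dose of study treatment. Take scheduled Day 1 samples as pre-dose. Treat unscheduled Day 1 tests as post-baseline unless a recorded time or label shows that they precede the dose.
2. **SAP 2.7.3.** Build the shift tables on the worst post-baseline value within the on-treatment period. This matches the liver summary in the same section.

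The second change should not be made alone. With SAP 5.1 unchanged, a post-dose Day 1 value would become the baseline and then drop out of the post-baseline values altogether.

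The cost is two sentences and a programming flag, with a small downside. Protocol 6.6.1 records "The date and time of all study treatment administration sabatolimab during the study", which names sabatolimab only, and Protocol 8.5.2.1 requires clock times for PK draws. Neither document shows that local laboratory draw times are collected. Without them, a genuine pre-dose unscheduled repeat could be classed as post-baseline, and Day 1 chemistry is assumed, not shown, to be pre-dose. A footnote counting participants with an untimed unscheduled Day 1 test would make this visible.
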